# 11 Study Data Collection and Monitoring

# 11.1 Data Management

This study will collect regulatory and clinical data using University of Minnesota CTSI's instance of OnCore® (Online Enterprise Research Management Environment). The OnCore database resides on dedicated secure and PHI compliant hardware. Key study personnel are trained on the use of OnCore and will comply with protocol specific instructions embedded within the OnCore.

Additional immune monitoring data about correlative laboratory samples generated by the Masonic Cancer Center Translational Therapy Laboratory (TTL) from the protocol-directed correlative research samples is stored in their Laboratory Information Management System (LIMS). The LIMS database application is also stored on a production server located in the UMN datacenter (WBOB) and is managed by the Academic Health Center

#### 11.2 Case Report Forms

Participant data will be collected using protocol specific electronic case report forms (e-CRF) developed within the University of Minnesota OnCore based on its library of standardized forms. The e-CRFs will be approved by the Principal Investigator and the Biostatistician prior to release for use. The Study Coordinator or designee will be responsible for registering the patient into OnCore at time of study entry, completing e-CRF based on the patient specific calendar, and updating the patient record until patient death or end of required study participation.

# 11.3 Data and Safety Monitoring Plan

The study's Data and Safety Monitoring Plan will be in compliance with the University of Minnesota Masonic Cancer Center's Data & Safety Monitoring Plan (DSMP), which can be accessed at https://z.umn.edu/dsmp.

For the purposes of data and safety monitoring, this study is classified as high risk (Phase I under a locally sponsored IND). Therefore the following requirements will be fulfilled:

- The Masonic Cancer Center Data and Safety Monitoring Council (DSMC) will review the study's progress quarterly with the understanding the Cancer Protocol Review Committee (CPRC).
- The Masonic Cancer Center PI will comply with at least twice yearly monitoring of the project by the Masonic Cancer Center monitoring services.

## 11.4 Regular Team Meetings to Review Safety

Regular meetings will be held to facilitate communication regarding the study's progress in terms of individual patient safety including events meeting the definition of dose limiting toxicity, excessive toxicity (early study stopping rule for CRM only), serious adverse events (SAEs) and overall impact on future enrollment.

At a minimum each patient is reviewed at the end the 1st 21 days to document the DLT status and to confirm the timing and dose level for the next patient cohort enrolled.

The outcome of these discussion will be documented in the meeting minutes and the statistician or designee will send out a confirmatory email summarizing the discussion which will become part of the regulatory record.

Other issues for discussion may include pending patients, patient updates, summary of safety reports, and case report form completion.

The CRC or CRC-RN or designee is responsible for arranging these meetings and preparing the agenda. Meetings will occur every 2 weeks; however, these may be scheduled more or less frequently at the discretion of the PI and/or study staff. The

safety discussion may be part of the regular PI meeting but must be documented as above (in study minutes and post-meeting email from the statistician or designee).

Expected participation includes the Principal Investigator, the study statistician or designee and relevant CTO staff (CRC-RN, CRC, Regulatory Specialist, and Program Manager) or appropriate designee.

In the situation of a patient completing the DLT period between scheduled meetings, communication via email may be used in lieu of a meeting provided the patient was discussed at the prior meeting and will be included on the next meeting's agenda.

#### 11.5 Record Retention

The Investigator will retain study records including source data, copies of case report form, consent forms, HIPAA authorizations, and all study correspondence in a secured facility until notified by the Masonic Cancer Center Clinical Trials Office that the study records may be destroyed.

# 12 Study Endpoints

# **12.1 Primary Endpoint**

The primary endpoint is identification of the maximum tolerated dose (MTD) for HCW9218.

# 12.2 Secondary Endpoints

The safety of repeat dosing of HCW9218 is adverse events (AEs) based on CTCAE v5.

Response and progression endpoints are based on the Response Evaluation Criteria in Solid Tumors (RECIST) 1.1.

- Response rate (CR, PR or SD) at 3 months, 6 months and 12 months
- Progression-free survival (PFS) by 6 month and 1 year is defined as the duration of time from start of treatment to time of progression or death, whichever occurs first
- Overall survival (OS) at 6 month and 1 year from 1st dose of HCW9218 is defined as patients alive at 1 year

## 13 Statistical Considerations

## 13.1 Study Design, Objectives and Endpoints

The purpose of this Phase I open-label study will be to identify the maximum tolerated dose (MTD) in a combined study group of all solid tumor cancers (except pancreatic cancer) and provide preliminary estimates of the response for future studies.

The primary endpoint is to provide the MTD of HCW9218 in advanced solid tumor cancers. The primary analysis will be intent-to-treat from the point of 1st injection of HCW9218 both for toxicity and efficacy. Patients who discontinue therapy prior to injection #1 will be replaced. We expect that the number of patients coming off therapy prior to injection #1 will be minimal/none.

There are 5 potential dose levels defined for Phase I. The trial will be conducted with no intra-patient escalation. The starting dose will be 0.25 mg/kg HCW9218 with a safety dose of 0.1 mg/kg HCW9218. The subsequent planned cohorts will be 0.5 mg/kg HCW9218, 0.8 mg/kg HCW9218 and 1.2 mg/kg HCW9218 (Table 1). Given that little to no toxicity is expected, the MTD will be determined using an adaptation of the continual reassessment method (CRM) (O'Quigley, 1996) starting with 1 patient cohorts.

Table 1.

Phase I HCW9218 Dose Levels					
Dose Level	HCW9218 dose				
-1	0.1 mg/kg				
1 (start)	0.25 mg/kg				
2	0.5 mg/kg				
3	0.8 mg/kg				
4	1.2 mg/kg				

This Phase I study will be conducted in two consecutive stages (non-CRM and CRM). A minimum of 21 days must separate each cohort. All patients are assessed for Dose Limiting Toxicity (DLT) per Section 6.3 as defined in the schema below:

**Stage 1 Step 1** uses a fast-track design (1 patient per cohort) with a minimum of 21 days between each patient until one of the following occurs:

The 1st occurrence of a **pre-defined treatment emergent adverse event** within 21 days of the 1st HCW injection (Section 6.2.1) at which point the study moves to **Step 2** and the cohort size increases from 1 to 3 patients with 2 additional patients added to the current cohort. A minimum of 21 days must separate each 3 patient cohort

- Escalation in Step 2 continues until the 1st DLT event at which point Stage 2
   (CRM) is activated. If Cohort 4 is completed without a DLT, Stage 2 (CRM) is not used.
- The 1st occurrence of a DLT at which point the study moves directly to Stage 2
  (CRM) as detailed below and Step 2 is not used.
- Cohort 4 is completed without a pre-defined AE or a DLT neither Step 2 nor Stage 2 is used if a total of 9 patients are enrolled in Cohort 4 to complete the study.

Stage 2 is initiated at the 1st DLT. The study design changes to an application of the continual reassessment method (CRM) with an informative skeleton based on constrained maximum likelihood estimation (lasonos & O'Quigley, 2012). Enrollment occurs in cohorts of three patients. Each new cohort of three patients are sequentially assigned to the most appropriate dose by the study statistician based on the updated toxicity probabilities once the 3rd patient in a cohort reaches Day 21 (DLT period). The goal will be to identify one of the 5 dose level strategies corresponding to the desired maximum toxicity rate of ≤25%. The MTD will be identified by the minimum of the following criteria: (1) the total Stage 2 sample size of 24 is exhausted or (2) 9 consecutive patients are enrolled at the same dose. The function 'crm' from the R package 'dfcrm' will calculate posterior means of toxicity probabilities. Dose escalation of more than one level is not permitted with this design.

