### **STAGE 2 Continual Reassessment Method (CRM)**

The study design changes to an application of the continual reassessment method (CRM). Enrollment occurs in cohorts of 3. Within a 3 patient dose cohort, a minimum of 14 days must separate the 1st and 2nd patient with no staggering of enrollment required between and 2nd and 3rd patient. Once the 3rd patient in a cohort reaches Day 21 (DLT period), a new cohort of 3 patients is sequentially assigned to the most appropriate dose by the study statistician based on the updated toxicity probabilities. The goal will be to identify one of the 4 dose levels corresponding to the desired maximum toxicity rate of ≤25%. The MTD will be identified by the minimum of the following criteria: (1) the total Stage 2 sample size of 24 is exhausted or (2) 9 consecutive patients are enrolled at the same dose.

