# **Study Schema**

1 cycle = 3 weeks (21 days) with a 2-cycle minimum unless medically contraindicated.

**HCW9218** at assigned dose by subcutaneous (SC) injection once every 3 weeks until disease progression, unacceptable toxicity, patient refusal, or felt to be no longer of benefit

Assess for Dose Limiting Toxicity (DLT) at Cycle 2 Day 1 (defined below and in Section 6.3)

tumor biopsy (baseline and prior to Cycle 3) – optional, in participants with accessible tumor who have signed the separate biopsy consent (Tumor used for biopsy should not be a RECIST target lesions unless there are no other lesions suitable for biopsy.)

Disease reassessment per disease specific standard of care (i.e. every 8-12 weeks)

Phase I HCW9218 Dose Levels			
Dose Level (DL)	HCW9218 dose		
-1*	0.1 mg/kg		
1 (start)	0.25 mg/kg		
2	0.5 mg/kg		
3	0.8 mg/kg		
4	1.2 mg/kg		

\* use only if excessive toxicity encountered at DL1

**Dose limiting toxicity (DLT)** is defined as any of the following **treatment emergent events** based on CTCAE v5 within 21 days after the 1st dose of HCW9218 as assessed on Day 22 (Cycle 2 Day 1) per Section 6.3.

DLT event	Exceptions:			
Any Grade 4 hematologic event	
 
Grade 4 lymphopenia that resolves to Grade 1 or lower (or to Baseline or lower, if pre-existing Grade 2 or higher) within 7 days
 
Grade 4 leukopenia that resolves to Grade 1 or lower (or to Baseline or lower, if pre-existing Grade 2 or higher) within 7 days
 
			
Any Grade 3 or Grade 4 febrile neutropenia				
Any Grade 3 thrombocytopenia with bleeding				
Any Grade 3 or higher non-hematologic adverse event	
 
Grade 3 nausea, vomiting and/or diarrhea that last < 72 hours
 
Grade 3 or higher electrolyte abnormality that lasts < 72 hours, is not clinically complicated, and resolves spontaneously or responds to conventional medical interventions
 
Isolated Grade 3 elevation of ALT and/or AST that resolves to Grade 1 or lower (or to Baseline or lower, if pre-existing Grade 2 or higher) within 7 days
 
Grade 3 amylase or lipase that is not associated with symptoms or clinical manifestations of pancreatitis
 
Grade 3 fatigue, not due to disease progression, that lasts < 1 week
 
			

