# 6.2.3 STAGE 2 Continual Reassessment Method (CRM)

The study design changes to an application of the continual reassessment method (CRM). Enrollment occurs in cohorts of three with a minimum of 14 days between the 1st and 2nd patient. Each new cohort of three patients are sequentially assigned to the most appropriate dose by the study statistician based on the updated toxicity probabilities once the 3rd patient in a cohort reaches Day 21 (DLT period). The goal will be to identify one of the 4 dose level strategies corresponding to the desired maximum toxicity rate of ≤25%. The MTD will be identified by the minimum of the following criteria: (1) the total Stage 2 sample size of 24 is exhausted or (2) 9 consecutive patients are enrolled at the same dose.

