### 6.3 Monitoring for Dose Limiting Toxicities and Excessive Toxicity

Toxicity and adverse events are classified and graded according to NCI's Common Terminology Criteria for Adverse Events V 5.0 (CTCAE) unless otherwise noted in Section 10.

Note during the fast-track dose escalation only (Stage 1, Step 1), patients also are monitored for the pre-defined treatment emergent events defined in Section 6.2.1.

**Dose Limiting Toxicity (DLT)** is defined as any of the following treatment emergent adverse events using the NCI Common Terminology Criteria for Adverse Events (CTCAE) Version 5.0 within the 21 days after the 1st dose of HCW9218:

DLT event	Exceptions:		
Any Grade 3 or Grade 4 febrile neutropenia Any Grade 3 thrombocytopenia with bleeding Any Grade 3 or higher non-hematologic adverse event	
 
Grade 4 lymphopenia hat resolves to Grade 1 or lower (or to Baseline or lower, if pre-existing Grade 2 or higher) within 7 days
 
Grade 4 leukopenia that resolves to Grade 1 or lower (or to Baseline or lower, if pre-existing Grade 2 or higher) within 7 days
 
Grade 3 nausea, vomiting and/or diarrhea that last < 72 hours
 
Grade 3 or higher electrolyte abnormality that lasts < 72 hours, is not clinically complicated, and resolves spontaneously or responds to conventional medical interventions
 
Isolated Grade 3 elevation of ALT and/or AST that resolves to Grade 1 or lower (or to Baseline or lower, if pre-existing Grade 2 or higher) within 7 days
 
Grade 3 amylase or lipase that is not associated with symptoms or clinical manifestations of pancreatitis
 
		
	
 
Grade 3 fatigue, not due to disease progression, that lasts < 1 week
 
		
Hy's Law case (i.e., alanine aminotransferase/ aspartate aminotransferase (ALT/AST) >3 x ULN in combination with total bilirubin level (TBL) > 2 x ULN in the absence of cholestatic injury (ALP < 2 x ULN (Ricart, 2017; FDA, 2009)) and no other cause identified) after excluding biliary tract obstruction and liver metastasis  Inability to receive Cycle 2 dosing due to treatment related toxicity	MORE - I WOR		

The Dose Limiting Toxicity (DLT) Observation Period is defined as 21 days after the first dose of HCW9218. The DLT period does not end until the patient is assessed on Cycle 2 Day 1 (+3 days) and the results of lab work drawn on Cycle 2 Day 1 (+3 days) confirms no new DLTs since the previous assessment.

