#### 8.1 Standard of Care Activities

Standard of care assessments and procedures are part of good clinical care and are charged to the patient and their health insurance.

	Baseline / screening Within 28 days of Cycle 1 Day 1 unless o/w noted¹	Cycle	1					Cycle	2				Cycle 3 and subsequent cycles	Every 4 cycles (12 weeks) or per SOC if more	End of treatment (EOT) visit 3 weeks after the last dose	After EOT visit: Follow-up for response until PD, then survival only every 3 mon
Study day	-28 to -1 (no Day 0)	1	2	3	5	8	15	1	2	5	8	15	1	frequent until PD	of HCW9218	for 12 months from C1D1
window	Not applicable	±1	day us	sing Day	1 as th	ne anch	or	+3 da	ys for I	Day 1	then ±	£1 day	±3 days	± 14 days	± 1 week	± 1 month
Written consent	X1															
Assess for eligibility	Х															
Medical history including prior cancer treatment	Х															
Concomitant medications	X	Х				Χ	Χ	Χ			Χ	Χ	Х		Х	
AE assessment		Χ	Χ	Х	Χ	Χ	Χ	Χ	Χ	Χ	Χ	Χ	Х		Х	
Physical exam 	Х	Χ				Χ		Χ					Х		Х	
Provider assessment	Х	Х			Χ	Χ	Χ	Χ					Х		Х	
ECOG Performance Status	Х	Χ				Χ		Χ							Х	
Vitals signs	Х	X 3	Χ	Х	Χ	Χ	Χ	X 3	Χ	Χ	Χ	Χ	X 		Х	
Weight  plus height at baseline only	X	X 				Χ		Χ				Χ	Х		X	
CBC with differential	X1	X 	Χ	Χ	Χ	Χ	Χ	Χ	Χ	Χ	Χ	Χ	X 		X	
Complete metabolic panel 	X 	X 				Χ		Χ					X 		Х	
CRP, ferritin, amylase, lipase, LDH, mg, phos	X8					X8										
Diagnosis related biomarker (e.g., CA125, PSA)	Х													Х		Х
Pulmonary function testing only if clinically indicated	Х															
Tumor assessment by disease appropriate methods	X 													Х		Х
Disease response based on RECIST 1.1 (until disease progression)	X 													Х		Х
Survival/follow-up																Х

1. Baseline/Screening – within 14 days of study treatment start for labs required for eligibility; prior disease assessments may be used if they were performed within 42 days of the 1st HCW9218 dose in the absence of intervening anti-cancer therapy. Consent is exempt from 28 day limit and may be performed at any time prior to starting study related activities. If more than 14 days pass between lab work for eligibility (found in Section 4.1.6) and Cycle 1 Day 1, the pre Cycle 1 lab results must continue to meet the criteria in Section 4.1.6.

March 29, 2023 Page 41 of 76 confidential

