2. Safety labs can be collected up to 72 hours prior to administration of HCW9218 except for C2 D1 where labs cannot be collected sooner than Cycle 1 Day 22 / Cycle 2 Day 1 (the end of DLT period).

3. C1D1 and C2D1: Vital signs (body temperature, heart rate, respiratory rate, systolic and diastolic blood pressure) are documented before each HCW9218 dose and then after dosing at 15 min (± 5 min), 30 min (± 5 min), 60 min (± 10 min) and 120 min (± 15 min) then hourly (± 15 min) until discharge from the clinic or at completion of dose monitoring.

4. For C3D1 and subsequent doses: Vital signs (body temperature, heart rate, respiratory rate, systolic / diastolic blood pressure) are documented before each HCW9218 dose and then after dosing at 15 min (± 5 min) and 30 min (± 5 min).

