#### CPRC #2021LS143 - HCW9218 for Select Advanced Solid Tumors

- 5. HCW9218 dose calculation is based on patient's dose level and actual body weight recorded at Day 1 (or within 14 days prior). Dose adjustments occur only if weight changes by ±10% or greater from weight used to calculate original dose per Section 4.1.
- 6. Cardiac function should be monitored by clinical examination and assessment of vital signs for hypotension, arrhythmia, angina and myocardial infarction. During the study, participants with signs or symptoms of chest pain, murmurs, gallops, irregular rhythm, or palpitations must be further assessed if clinically indicated, including the need for hospitalization
- 7. Complete metabolic panel includes: albumin, alkaline phosphatase, ALT, Anion gap, AST, bilirubin (total), calcium, chloride, CO2, creatinine, glucose, potassium, protein (total), sodium, urea nitrogen
- 8. Baseline and Day 8 measures, repeat only if clinically indicated.

March 29, 2023 Page 42 of 76 confidential

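### Stage 2 lets the next cohort be assigned at Day 21, but Section 6.3 keeps the DLT period open until the Cycle 2 Day 1 assessment and labs, Day 22 at the earliest

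*Combined protocol and SAP*

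**What the plan says.** **The trigger.** The Synopsis (Stage 2) reads: "Once the 3rd patient in a cohort reaches Day 21 (DLT period), a new cohort of 3 patients is sequentially assigned". Section 6.2.3 has the same trigger, when the third "patient in a cohort reaches Day 21 (DLT period", and Section 13.1 repeats it: "once the 3rd patient in a cohort reaches Day 21 (DLT period".

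**The closure of the DLT period.** Section 6.3 sets a 21-day observation period and then adds: "The DLT period does not end until the patient is assessed on Cycle 2 Day 1 (+3 days". It also requires the results of labs drawn at that visit to show no new DLT. The Study Schema describes DLTs "as assessed on Day 22 (Cycle 2 Day 1) per Section 6.3". Section 8.1, footnote 2, says that at this visit "labs cannot be collected sooner than Cycle 1 Day 22 / Cycle 2 Day 1 (the end of DLT period".

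**The stopping rule.** The Schema and Section 13.4 update the posterior at the end of a 21-day evaluation period. The monitoring paragraph in Section 6.3 speaks instead of the 21-day DLT period.

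**The concern.** The CRM picks the next dose from the DLT count. If the count is taken on Day 21, two kinds of DLT can still be missing for the most recent patients: a laboratory DLT first seen in the Cycle 2 Day 1 sample, and the criterion of being unable to receive Cycle 2 because of treatment-related toxicity. The second cannot be known before Cycle 2 Day 1. An incomplete count can only be too low, so any error points towards a higher dose for the next three patients. It also arises in the stage that is opened because toxicity has been seen.

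**Working it through.** **1. Calendar.** Section 8.1 counts the first dose as Day 1 and has no Day 0.
- 21 days after the first dose: 1 + 21 = Day 22. This reproduces the Schema's own day for the DLT assessment.
- Section 6.3 closure with the +3 day window: Day 22 to Day 25, plus lab turnaround.
- Gap after the trigger: 22 − 21 = 1 day, up to 25 − 21 = 4 days, plus lab turnaround.

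**2. What is open on Day 21.** In the Section 8.1 schedule, the row "Complete metabolic panel" is marked in Cycle 1 only on Days 1 and 8; the next mark is Cycle 2 Day 1. Footnote 7 shows what it carries: "Complete metabolic panel includes: albumin, alkaline phosphatase, ALT, Anion gap, AST, bilirubin (total), calcium, chloride", among others. These include the transaminase, ALP and bilirubin values that the Hy's Law and ALT/AST criteria need. From Day 8 to Day 21 is 13 days with no scheduled panel. The CBC is scheduled through Day 15.

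**3. Who can be open.** The Synopsis and Section 6.2.3 keep at least 14 days between patients 1 and 2. When patient 3 reaches Day 21, patient 1 is at Day 21 + 14 = 35 or later. On the ordinary calendar, only patients 2 and 3 can be incomplete.

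**4. Does one missing DLT matter to the CRM?** This is an illustration only, because the documents give no final skeleton or prior. Assumptions:
- Power model, skeleton raised to exp(b), with b normal, mean 0 and variance 0.5, 1.34 or 3.0. The posterior mean of b is plugged in. There are five doses, the target is 25%, and escalation is by at most one level.
- Six skeletons: the two sets of DLT probabilities in Table 2, and four indifference-interval skeletons (half-width 0.05 or 0.08, prior MTD at the third or fourth dose).
- Starting data: the Revision History (March 29 2023) reports no DLT from dose level 1 to 4 but gives no patient counts. So DL1 to DL3 have 0/k each with k = 1 or 3, and the first DLT occurs in the m-th DL4 patient, m = 2 to 9.
- The model picks the dose for the next three patients. That cohort is then counted as 0/3 (DLT missed) or 1/3 (DLT seen).

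This gives 8 values of m × 6 skeletons = 48 runs per cell. Runs in which the recommended dose changed:

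| Prior variance | k=1, closest to 25% | k=1, highest ≤25% | k=3, closest to 25% | k=3, highest ≤25% | Total of 192 |
|---|---|---|---|---|---|
| 0.5 | 10 | 24 | 2 | 11 | 47 |
| 1.34 | 8 | 19 | 0 | 7 | 34 |
| 3.0 | 5 | 19 | 0 | 4 | 28 |

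At variance 1.34, 192 − 34 = 158 runs (82%) do not change. In every run that changes, at all three variances, the incomplete count gives the higher dose. At variance 1.34, the next three patients would go above the current cohort's dose in 7 of 8, 9 of 19 and 3 of 7 of the changed runs. The highest posterior probability of a DLT rate above 25% at that variance is 0.070 for DL −1 and 0.123 for DL1, against the 0.80 stopping threshold. It stays far below 0.80 at the other two variances.

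**The case against.** The best defence is that each trigger carries the label DLT period, and Section 6.3 defines when that period ends. Section 13.1 assesses all patients for DLT per Section 6.3, and Sections 8 and 8.1 label Cycle 2 Day 1 the end of the DLT period. The first column of the Section 10.2 table, not limited by stage, runs until the DLT assessment is complete. Section 11.4 has DLT status documented and the next dose level confirmed, and refers to patients completing the DLT period between meetings. Section 14.1 treats timeframes as targets unless the word must is used, so waiting a day or more breaches nothing.

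Much of this stands. It makes waiting permissible and likely, and a reader should not infer that the plan obliges the team to assign on incomplete data. But none of these places makes the CRM update wait. Three sections name Day 21. Section 11.4 sets its minimum review at the end of the first 21 days without requiring the Cycle 2 Day 1 labs. The footnote in Section 10.2 that links DLTs to cohort decisions does so for Stage 1. For the stopping rule, the paragraph in Section 6.3 read with its own closure definition does wait, while the Schema and Section 13.4 are ambiguous.

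It is also fair that the CRM counts depend on assumptions. They move with the prior variance, and no assumed skeleton was built by the constrained maximum likelihood method that Section 13.1 names. They show direction and sensitivity, not the trial's operating characteristics.

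**Conclusion.** The inconsistency is real and should be fixed. The stated trigger precedes DLT closure by 1 day, or up to 4 if the visit window is used, plus lab turnaround. Followed literally, it can feed an incomplete count into one assignment of three patients.

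The consequence is limited. Stage 2 runs only after a first DLT. The CRM is cumulative, so a late DLT enters the next update. The MTD is touched indirectly, or directly only if the last cohort is read early. The probability of a missed DLT cannot be derived from the documents, and the illustrative runs assume that one was missed.

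Two stronger readings are not supported:
- *The gap is 8 to 11 days.* Section 6.1.1 allows Cycle 2 to be held for up to a week, which would put the decision at Day 29 to 32 (22 + 7 to 25 + 7). But Section 6.3 does not say whether a hold extends the DLT window, so this is inference.
- *A missed DLT could defeat the stopping rule.* A scenario starting from a first DLT at DL2 can be made to cross the 80% threshold, but the Revision History reports no DLT from DL1 to DL4. Starting from that state, the threshold is not approached in the runs above.

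**What to change.** Reconcile the Day 21 wording in the Synopsis (Stage 2), Sections 6.2.3 and 13.1, the 21-day review in Section 11.4, and the 21-day evaluation period in the Schema and Section 13.4 with the closure in Section 6.3, the Day 22 assessment in the Schema and footnote 2 of Section 8.1. One sentence would do: the CRM update, the stopping-rule update and the assignment of the next cohort use DLT status as determined under Section 6.3 for every patient in the current cohort.

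The sponsor should also reconcile how a held Cycle 2 (Section 6.1.1) fits the DLT window. No clinical rule is proposed here.

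The cost is wording, plus normally 1 to 4 days and lab turnaround per Stage 2 cohort. If Stage 2 ran to 24 patients, there would be 24/3 = 8 cohorts and 7 decisions between them, so 7 × 1 = 7 to 7 × 4 = 28 days in all, plus turnaround. The sample size, target rate and dose levels do not change.
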